5.3 Informed Consent Procedures

Patients

We will provide potential patients a *Patient Study Information Document* (Appendix B.5 Recruitment Materials: Patient Study Information Document) either by mail or a link to an online version of the *Patient Study Information Document* for them to review and download (<https://redcap.link/CKMjumpstart>). The *Patient Study Information Document* describes the study procedures, risks, and benefits, and information on what to do and expect if they decide not to participate. We will provide this link verbally over the phone and read aloud the study information document. A copy of the *Patient Study Information Document* can also be downloaded from the webpage. For those who prefer to first review a mailed a paper copy of the *Patient Study Information Document* before deciding whether to participate, we will follow-up by phone in about 1 week after the mailing.

The *Patient Study Information Document* will be hosted on UW REDCap, however UW REDCap will not be used for the storage or analysis of any VA data, and no VA data will be shared with UW REDCap. The only use of UW REDCap in this study is to use the provided link to disseminate an information sheet that does not require patients to enter any information or to provide their electronic consent.

Because the study procedures and intervention poses minimal risk to patients, and many patients prefer to complete study procedures remotely, we are requesting a waiver of written informed consent from patients to participate in the study. To ensure informed consent, we will use a “*Teach-back Method*” (see Appendix B.6. Recruitment Materials: Patient Teach-back Exercises) in which, after reviewing the study, we will ask patients a series of true/false questions about key aspects of the study aims, procedures and potential risks and benefits. Any responses that are incorrect or incomplete will be reviewed with patients, and they will be asked for responses to missed statements for a second time. We will repeat this teach-back approach a second time if there are aspects of the study that are still not understood by patients. Patients whose responses to statements are still incorrect after three responses would be considered to have inadequate understanding of the study and to be ineligible to participate.

Patients will be informed that participation is fully voluntary and that their decision regarding participation will in no way affect their access to services or the quality of care they receive at the VA, and that their identifiable information will not, at any time, be linked to the digitally recorded interview or the subsequent transcript.

Providers

Because the study procedures and intervention pose minimal risk to providers and that intervention is intended to promote standard of care (i.e. discussion of available treatment options for advanced CKD with patients), we are requesting a waiver of written informed consent from providers to participate in study interviews. We will review the study with providers using a standard script (Appendix B.7. Recruitment Materials: Provider Consent Script), which will cover the aims of the study, study procedures, and potential risks and benefits. They will also receive a study information document (Appendix B.8: Provider Study Information Document) when they are provided the CKM JumpStart tool in an encrypted email.

5.4 Inclusion/Exclusion Criteria

Patients

Inclusion:

- Adults aged ≥ 75 years
- Advanced CKD as defined as having at least 2 outpatient measures of eGFR < 25 ml/min/1.73m² separated by > 90 days in the prior year and with at least 1 eGFR measure < 20 .
- English-speaking
- Receive care from a provider at UW Medicine or VAPSHCS
- Open to discussing their values and treatment options for kidney disease with their provider.

Exclusion:

- Unable to complete the informed consent process
- Currently receiving maintenance dialysis

Providers

Inclusion

- Their patient is a participant in the study.
- Are a UW Medicine or VAPSHCS provider or trainee.

Exclusion

- None

5.5 Study Evaluations

Patients

The date of study enrollment will be the date that a patient's consent is obtained. Patients will be followed through patient's death, date of study withdrawal, or study completion, whichever is earliest.

Patients will complete the following surveys and interviews at enrollment (T1), within 2 weeks of their following clinic visit with their provider (T2), and about 3 months after this clinic visit (T3). All study procedures will be conducted by phone. Each phone call will take a total of 15 to 30 minutes. We will give participants a \$20 gift card for each study visit that they complete. Gift cards will be mailed within five business days of a completed call.

Demographic survey (Appendix C.1): At T1, patients will be asked their gender, age, race, prior education, total annual household income, current employment status, and self-rated overall health.

EuroQol 5D (Appendix C.2): At T1, patients will be asked to complete a 5-item survey inquiring different domains of quality of life, including mobility, self-care, usual activities, pain/discomfort, and anxiety/depression, on a 5-point scale.²⁴

Control Preferences Scale (Appendix C.3): At T1, using a single question, patients will be asked to rate on a 5-point scale their preference in taking lead in medical decision-making.

Healthcare values (Appendix C.4): At T1, using a single validated question, we will ask patients about their preference for either extending life or preserving comfort. Patients will also have the option of indicating that they are uncertain about which they prefer. We will also ask whether they perceive that their provider provides care that is mostly directed at extending life or preserving comfort or are unsure. Patients will be considered as receiving goal concordant care if they perceive the care that they receive matches the care that they value.

Quality of communication (Appendix C.5): At T1, T2 and T3, patients will be asked to rate the quality of serious illness communication with their providers using the 13-item subscale of the Quality of Communication Questionnaire.²⁵⁻²⁷

Discussion of treatment options (Appendix C.6): At T1, patients will be asked if they had ever discussed CKM and dialysis with their provider. At T2 and T3, patients will again be asked if they had discussed these topics since the last study visit.

Decisional conflict (Appendix C.7): At T1, T2 and T3, patients will be asked to complete the 4-item SURE Test to assess their preference for dialysis vs. CKM and the decisional conflict they have about their options.^{28,29}

Post-clinic patient interview (Appendix C.8): At T2, patients assigned to the intervention will be invited to answer 4 open-ended questions about their clinical encounter with their provider. Questions will pertain to topics discussed during the encounter with their clinician, whether their provider asked them about their values, whether CKM was discussed, and their perception of CKM based on the conversation. Interviews will be audio-recorded then transcribed. We estimate that an interview will take 10-15 minutes to complete.

Documentation of discussion of CKM with patients: At T2 and T3, we will review each patient's recent nephrology clinic notes to determine whether providers documented a discussion with patients about CKM. Documentation will be transcribed into a Word document without personal identifiers.

Providers

Demographic information: From publicly available directories, we will ascertain providers' gender, race, and years since completing their medical degree.

Use of the CKM Jumpstart Tool (part of Appendix B.3): For providers whose patients were assigned to the intervention, we will ask them after their visit with their enrolled patient (T2) whether they had used the CKM Jumpstart Tool during their visit, and if not their reasons for not using the Tool.

Post-clinic provider interview (Appendix C.9): For providers who used the CKM Jumpstart Tool, we will ask 4 open-ended questions about their clinical encounter with the patient and their experience using the CKM JumpStart Tool. Clinician responses will be recorded in writing, then transcribed into a Word document. We estimate that an interview will take 5 minutes to complete. Interviews will be conducted by phone or in-person in a private clinic room or office of the provider, per the provider's preference. Providers will be offered a \$10 gift card for their participation.

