3.0 Objectives

We aim to conduct a randomized pilot study to test the feasibility and acceptability of a novel communication tool, called The CKM JumpStart Tool, and explore preliminary outcomes, including decisional uncertainty and goal concordant care to inform a future clinical trial. We hypothesize that the decision aid will be feasible and acceptable to patients and their providers.

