situation permits. We will share the CKM Jumpstool with their provider by encrypted email (Appendix A.2. Intervention Materials: Provider Email Notification) prior to the visit. The email will contain a link to a brief video demonstrating the use the CKM JumpStart Tool (bit.ly/CKMJumpstart) and an attachment which describes the study in more detail (Appendix B.8: Provider Study Information Document). We will also provide the providers with a paper copy of the CKM JumpStart Tool on the day of their visit with the patient and remind them how to use the CKM JumpStart Tool using a standard script (Appendix A.3. Intervention Materials: Provider Script Notification). In both in email and in-person, we will assure the provider that they are not obligated to use CKM JumpStart Tool or discuss their patient's values and CKM and that they are free to do so if they choose. We will also assure the provider that the patient consented to a potential discussion of their values and CKM if it should arise during their clinic visit.

Usual care

Patients randomized to usual care will also will be surveyed at T1 but **will not** have a CKM JumpStart Tool generated describing their values and their response to the values question will not be shared with their providers. They will receive care as they usually do from their provider.

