5.3 Recruitment Methods

We aim to enroll up to 76 patients with advanced CKD and up to 30 of their providers in this study.

Patients

We are requesting a waiver of consent and HIPAA authorization to access the electronic medical records of patients to identify eligible patients for this study and to obtain their name and contact information for recruitment purposes only.

We will mail an *Introductory Letter* (see Appendix B.1: Recruitment Materials: Patient Introductory Letter) introducing the study. We will then follow up with a phone call about 1 week later to confirm that patients receive the letter, introduce the study, and determine if they are interested in participating in the study using a standard script (see Appendix B.2. Recruitment Materials: Patient Introductory Script).

We will not make more than 3 attempts to reach each patient by phone after mailing the introductory letter.

Providers

For enrolled patients who are randomized to the intervention, we will approach their providers in-person after their visit with their enrolled patients to inquire whether they had used the CKM Jumpstart Tool during their visit with the patient, and if so, invite them to participate in a brief phone or in-person interview about their experience using the CKM JumpStart Tool. We will use a standard script to recruit providers (Appendix B.3 Recruitment Materials: Provider Recruitment Script). If providers are unavailable to speak after the clinic visit, we will approach providers using encrypted email within 1 week after the clinic visit (Appendix B.4. Recruitment Materials: Provider Recruitment Email) and invite them complete an interview. We are requesting a waiver of informed consent to inquire providers if they had used the CKM Jumpstart Tool during their visit and the primary reason for not using the Tool to determine providers' eligibility to participate in the study.

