5.6 Data Analysis

Feasibility and acceptability: As our primary outcome, and measure of feasibility, we will compare the proportion of patients in each study arm who reported having discussed CKM with their provider at T2 and T3. Based on prior work, the rate of patient-reported discussion of CKM with their health care providers in usual care settings is approximately 3%. The target sample size (n=76) is estimated to provide 80% power (two tailed, $\alpha=0.05$) to detect an absolute difference of 25% or more in rates of patient-provider discussion of CKM between the intervention and control groups assuming a 30% attrition rate. We will also evaluate the proportion of patients in each arm who has documentation in their nephrology clinic notes that CKM was discussed with the patient at T2 and T3.

As a measure of acceptability, we collect attrition rates at T2 and T3. We will further assess user experience of the CKM JumpStart by performing a qualitative analysis of post-intervention interviews with patients and providers, coding for themes elucidating pros, cons and other considerations with using the CKM JumpStart Tool and discussion about CKM.

Exploratory outcomes: We will assess change (i.e., T3-T1 and T2-T1) in decision conflict about treatment decisions for advanced CKD and quality of communication scores. We will also assess change in the proportion of patients who reported receiving goal concordant care at each study time point based on patients.

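### The provider interview is limited to providers who used the Tool, so the provider acceptability conclusion is conditioned on use, and the recorded reasons for non-use have no role in the analysis

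*Protocol*

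**What the plan says.** Section 3.0 (Objectives) states the hypothesis for both groups: "We hypothesize that the decision aid will be feasible and acceptable to patients and their providers". Section 5.1 (Study arms) has staff assure providers that "they are not obligated to use CKM JumpStart Tool", so some non-use is expected by design.

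Under section 5.5, providers of intervention patients are asked after the visit "whether they had used the CKM Jumpstart Tool during their visit, and if not their reasons for not using the Tool". The interview is narrower: "For providers who used the CKM Jumpstart Tool, we will ask 4 open-ended questions". The Recruitment Methods section (5.3) applies the same gate. Staff ask about use, "and if so, invite them to participate in a brief phone or in-person interview about their experience using the CKM JumpStart Tool". That section seeks a consent waiver for asking about use and "the primary reason for not using the Tool to determine providers' eligibility to participate in the study", so it presents the question as an eligibility screen.

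Section 5.4 lists two provider inclusion criteria. One is "Their patient is a participant in the study"; the other is being a provider or trainee at one of the two sites. Tool use is not a criterion, and there are no provider exclusions.

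Section 5.6 introduces patient-reported CKM discussion by arm with "As our primary outcome, and measure of feasibility" and adds chart-documented discussion. For acceptability it names attrition at T2 and T3 and a qualitative analysis of patient and provider interviews. It mentions neither Tool use nor reasons for non-use.

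**The concern.** A provider who finds the Tool unsuitable and puts it aside is a likely source of unfavourable opinion, and the interview rule leaves that provider out for that visit. Themes about advantages and drawbacks would then come from encounters in which the provider had already judged the Tool worth using. If the pilot reports that providers find the Tool acceptable, readers planning the later trial may apply that to all providers who would be handed it. The evidence would support it only for visits where the Tool was used.

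An SAP, if one exists, could add a table of Tool use. It could not recover interviews that the protocol never offered.

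**Working it through.** The protocol gives no figure on this point to reproduce. The check is a comparison of sections, followed by an illustration of size.

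**Which provider data reach the acceptability analysis**

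| Source | Who supplies it | Role in section 5.6 |
|---|---|---|
| Attrition at T2 and T3 | Patients (these are patient study visits) | Acceptability |
| Post-clinic patient interview | All intervention patients are invited | Acceptability, qualitative |
| Post-clinic provider interview | Only providers who used the Tool | Acceptability, qualitative |
| Tool use, yes or no | Providers of intervention patients | None stated |
| Reasons for non-use | Those who did not use it | None stated |

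The only provider row with a role in the analysis is the one conditioned on use. The restriction does not affect patients.

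**Consistency of provider eligibility**

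Recruitment Methods and section 5.5 require Tool use before an interview. Section 5.4 does not require it and excludes nobody. A non-user therefore meets the listed criteria but is never invited.

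**Size**

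- Intervention visits: 76 patients randomised 1:1 gives 76/2 = 38, counting one index visit per patient and no losses.
- Uptake: not given in the protocol, so three counts are assumed.
- Share of visits with no provider interview: (38 − k)/38, where k is the number of visits with use. This assumes that every user accepts the interview.
- Wilson 95% interval for uptake p = k/n: [p + z²/(2n) ± z·√(p(1−p)/n + z²/(4n²))] / (1 + z²/n), with n = 38 and z = 1.96.

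For k = 19, z²/n = 3.84/38 = 0.101. The centre is (0.5 + 0.0505)/1.101 = 0.50. The half-width is 1.96 × √(0.00658 + 0.00067)/1.101 = 0.15.

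| Assumed use | Uptake (95% CI) | Visits with no provider interview |
|---|---|---|
| 10/38 | 26% (15% to 42%) | 28/38 = 74% |
| 19/38 | 50% (35% to 65%) | 19/38 = 50% |
| 28/38 | 74% (58% to 85%) | 10/38 = 26% |

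The intervals treat visits as independent. A provider may see more than one enrolled patient, and clustering of use by provider would widen them.

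**The case against.** **The interview is about using the Tool.** Section 5.6 presents it as a study of how the Tool is experienced in use, and asking only users is coherent for that purpose. This stands, but the conclusion must then be limited to users, and section 3.0 does not limit it.

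**Non-users are not unheard.** Their reasons are recorded. The gate also works visit by visit, so an interviewed provider may have been a non-user with another patient. Some non-use will reflect circumstances rather than disapproval. All of this stands. It is a reason to analyse the recorded reasons, and section 5.6 does not do so.

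A reader might infer three stronger things that the protocol does not support.

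- *Uptake is the true feasibility measure and the primary outcome is wrong.* The protocol may choose CKM discussion, because prompting that conversation is the Tool's stated purpose and the sample size rests on it. Chart-documented discussion is evaluated as well. Omitting a table of uptake from section 5.6 would not be a fault by itself, since an SAP commonly supplies one.
- *A null primary result could not be interpreted.* Tool use is recorded for intervention visits, and intervention patients are invited at T2 to say whether values and CKM came up. The data can help separate a tool that was not used from one that was used without effect.
- *Low uptake makes the powered effect implausible.* If discussion stays at 3% without the Tool, reaching 28% overall at uptake u needs a rate among users of (0.28 − 0.03(1 − u))/u. That is (0.28 − 0.015)/0.5 = 53% at u = 0.5 and (0.28 − 0.021)/0.3 = 86% at u = 0.3. The arithmetic is right, but both uptake values are assumed. The 3% rate is doubtful too, because every intervention provider gets an email, a video link, a paper copy and a reminder, and the outcome also counts discussions reported at T3.

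**Conclusion.** The point holds in a limited form. The protocol fixes a provider interview for users only, makes it the sole provider evidence on acceptability, and states its hypothesis for providers generally while making use optional. The provider conclusion is therefore conditioned on use, probably in the favourable direction. The direction assumes that non-users are on average less favourable than users, which is reasonable but not shown in the protocol. The size depends on uptake: under the assumed counts, between about a quarter and three quarters of intervention visits would contribute no provider interview.

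The primary outcome, its comparison between arms and the patient interviews are unaffected. This is a low-cost improvement to a pilot that already collects most of what it needs.

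**What to change.** 1. Keep patient-reported CKM discussion as the primary outcome.
2. In section 5.6, add the proportion of intervention visits at which the Tool was used. Take all intervention visits as the denominator, give a 95% confidence interval, and note that the same provider may appear more than once.
3. In section 5.6, analyse the recorded reasons for non-use as provider acceptability data alongside the interviews.
4. Either open a short interview to non-users, with questions adapted to non-use because the present ones concern experience with the Tool, or state that the provider acceptability conclusion applies to users only.
5. Reconcile the use requirement in Recruitment Methods and section 5.5 with the provider criteria in section 5.4.

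The use and non-use data are already collected, so items 2 and 3 need no new data. The waiver wording in Recruitment Methods ties the question to eligibility and would need a small amendment, as would the provider script. If non-users are interviewed, each interview costs about 5 minutes and a $10 card. At 19 non-use visits, with everyone accepting, that is 19 × 5 = 95 minutes and 19 × $10 = $190. The ceiling of 30 providers should be checked against the wider invitation. Some non-users will decline, so selection would be reduced but not removed.

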5.6 Data Analysis

Feasibility and acceptability: As our primary outcome, and measure of feasibility, we will compare the proportion of patients in each study arm who reported having discussed CKM with their provider at T2 and T3. Based on prior work, the rate of patient-reported discussion of CKM with their health care providers in usual care settings is approximately 3%. The target sample size (n=76) is estimated to provide 80% power (two tailed, $\alpha=0.05$) to detect an absolute difference of 25% or more in rates of patient-provider discussion of CKM between the intervention and control groups assuming a 30% attrition rate. We will also evaluate the proportion of patients in each arm who has documentation in their nephrology clinic notes that CKM was discussed with the patient at T2 and T3.

As a measure of acceptability, we collect attrition rates at T2 and T3. We will further assess user experience of the CKM JumpStart by performing a qualitative analysis of post-intervention interviews with patients and providers, coding for themes elucidating pros, cons and other considerations with using the CKM JumpStart Tool and discussion about CKM.

Exploratory outcomes: We will assess change (i.e., T3-T1 and T2-T1) in decision conflict about treatment decisions for advanced CKD and quality of communication scores. We will also assess change in the proportion of patients who reported receiving goal concordant care at each study time point based on patients.

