5.1 Study arms

Patients will be randomized in a 1:1 fashion using a random number generator (www.randomizer.org) to either 1 of 2 groups, CKM Jumpstart Tool or Usual Care. All enrolled patients will complete surveys within 2 weeks of their following clinic visit with their provider (T2), and about 3 months after this clinic visit (T3). All study procedures will be conducted either by phone or in-person, at the patient's convenience. Each visit will take about 20 minutes.

The CKM JumpStart Tool

The CKM JumpStart Tool is a 1-page handout that describes the values of a patient and words that a provider can try with the patient to explore the patient's values more and to provide a values-based introduction to CKM. The values describes in the CKM JumpStart Tool is based on a patient's response to a single validated question that asks the patient, if they had to choose, do they value care directed at longevity or comfort. A patient may also indicate whether they are unsure what kind of care they value more. Because there are 3 potential responses to the values question (longevity, comfort, unsure), there are 3 different versions of the CKM JumpStart Tool. (Appendix A.1 Intervention Materials: CKM JumpStart Tool Versions). The CKM JumpStart Tool does not contain any identifying information about the patient.

Patients who are randomized to receive the CKM Jumpstart Tool will be surveyed at T1. Using the patient's answer to the values question, study staff will generate a CKM JumpStart Tool prior to their upcoming clinic visit with their provider. Study staff will inform the patient that their response to the values question will be shared with their provider prior to their next clinic visit and that their providers might bring up their values and treatment options for kidney disease, if the

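### The powered primary outcome is set at T2 and T3 without saying which comparison is primary, and a separate T3 proportion would leave out the clinic visit at which the Tool is delivered

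*Protocol*

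**What the plan says.** Section 5.6 of the protocol names the primary outcome, which also serves as its feasibility measure: "we will compare the proportion of patients in each study arm who reported having discussed CKM with their provider at T2 and T3". One power statement follows. It assumes that "the rate of patient-reported discussion of CKM with their health care providers in usual care settings is approximately 3"% and claims 80% power, two-sided at 0.05, with 76 patients and 30% attrition, "to detect an absolute difference of 25% or more in rates of patient-provider discussion of CKM between the intervention and control groups". No time point or recall period is attached to the 3%, to the 25-point difference or to the 30%.

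Section 5.5 describes the item behind this outcome. At T1 it asks whether CKM was ever discussed. After that, "At T2 and T3, patients will again be asked if they had discussed these topics since the last study visit". T2 falls within two weeks of the next clinic visit and T3 about three months after that visit. The T2 patient interview in the same section is about that encounter, so T2 follows the visit.

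Section 5.1 ties the intervention to that one visit: "study staff will generate a CKM JumpStart Tool prior to their upcoming clinic visit with their provider". The provider also receives a "paper copy of the CKM JumpStart Tool on the day of their visit with the patient". No later delivery is described.

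**The concern.** A comparison at T2, a comparison at T3 and a comparison of any discussion by T3 are three different outcomes. The protocol powers one comparison and does not say which.

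This would matter little if the T3 item included everything the T2 item covered, but it does not. The visit before T3 is T2, so a patient who completed T2 is asked at T3 only about the time after T2. Suppose the Tool prompts a CKM discussion at the index visit and the subject is not raised again in the next three months. That patient is a yes at T2 and a no at T3, although the intervention did what it was meant to do.

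The trial could therefore end with a clear difference at T2 and a T3 proportion close to control, with no stated rule for which is the primary result. The pilot is meant to inform a later trial (sections 3.0 and 5.0), so the rate carried forward should be one whose meaning is fixed.

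**Working it through.** **1. Reproducing the stated sample size.** Inputs from section 5.6: 3% against 3% + 25 points = 28%, two-sided alpha 0.05, power 80%, 30% attrition, 76 patients; 1:1 allocation from section 5.1.

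- Arcsine effect size: h = 2·asin(√0.28) − 2·asin(√0.03) = 1.1152 − 0.3482 = 0.767.
- Per arm: n = 2·((1.960 + 0.842)/h)² = 26.7.
- Total randomised: 2 × 26.68 / 0.70 = 76.2, against 76 stated.
- Evaluable per arm from 76: 38 × 0.70 = 26.6. Power = Φ(0.767·√(26.6/2) − 1.960) = 79.9%.

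So 76 is right for one comparison of 28% with 3%.

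**2. Exact power for that comparison.** Section 5.6 names no test. I assume the uncorrected chi-square test, because its exact power agrees with the stated 80%. Summing binomial probabilities over all tables with two-sided p ≤ 0.05 gives 79.1% at 26 per arm and 80.9% at 27.

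**3. What each report covers for a patient who completes all visits.**

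| Report | Period asked about | Index visit included? |
|---|---|---|
| T1 | ever, up to enrolment | no |
| T2 | T1 to T2 | yes |
| T3 | T2 to T3 | no |
| T2 or T3 | T1 to T3 | yes |

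**4. Power of a separate T3 proportion.** The protocol gives no rate of new discussions after T2, so the intervention rates here are assumed; control is kept at 3%. Same exact calculation:

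| Intervention rate after T2 (assumed) | 26 per arm | 27 per arm | 30 per arm | 34 per arm |
|---|---|---|---|---|
| 8% | 7.4% | 8.0% | 9.9% | 12.3% |
| 10% | 13.3% | 14.2% | 17.0% | 20.7% |
| 15% | 32.7% | 34.4% | 39.2% | 45.0% |
| 20% | 53.4% | 55.4% | 60.8% | 67.0% |

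The 30 and 34 columns are there because section 5.6 does not say when the 30% attrition applies. For comparison, 28% against 3% has 84.6% and 89.0% power at those sizes. The gap remains.

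**5. Power of a cumulative outcome by T3.** Take 26 per arm, 28% against 3% at T2, assumed intervention rates after T2 of 3% to 20%, and 3% in control.

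- Independent reports: control 1 − 0.97² = 5.9%; intervention 1 − 0.72 × (1 − rate) = 30.2% to 42.4%; power 68.3% to 92.4%.
- No patient says yes twice: control 3% + 3% = 6%; intervention 31% to 48%; power 70.2% to 96.7%.
- Every T3 yes repeats a T2 yes: 28% against 3%; power 79.1%.

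A cumulative outcome may have more or less than 80% power, depending on overlap and on the period to which the 3% refers.

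**6. False-positive rate.** With 3% in both arms, the exact type I error of the assumed test at 26 to 27 per arm is about 0.7%. Two such tests together cannot exceed 2 × 0.7% = 1.4%.

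**The case against.** The strongest reply is that the T3 item is not faulty. The three reports cover successive periods without overlap, and together they cover the whole of follow-up. The wording can be read as a combined report or as two proportions shown side by side, and the data collected will support any of these definitions. Nothing is lost; one sentence is missing. The study is also a pilot, the outcome is labelled feasibility, and no go/no-go rule turns on T2 versus T3. All of this stands, and it keeps the weight low. It does not remove the point: section 5.6 plans a powered two-sided comparison, and the combined reading is not written there. The choice of primary comparison belongs to the outcome definition that the protocol itself states and powers, so it is not a detail commonly left to an analysis plan.

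Three stronger readings are tempting, and the document does not support them.

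- A reader might infer that two tests at 0.05 inflate the false-positive rate. If control is near the stated 3%, the assumed test is far below its nominal level (step 6), so this is not the concern.
- A reader might infer that 76 patients is wrong. It reproduces. The T3 power figures rest on assumed rates and show only that the stated power need not apply to T3.
- A reader might infer that T3 mixes recall periods, because a patient who missed T2 would answer back to T1. That depends on the wording in Appendix C.6, which is not shown, and on how many patients miss T2 but answer T3, which the protocol does not state.

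**Conclusion.** The point holds as a minor one. The protocol attaches one power statement to an outcome at two time points and does not say which comparison it belongs to. Under its own recall wording, a separate T3 proportion records an index-visit discussion as a no, for patients who completed T2, unless it was repeated.

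The stated 80% fits a single comparison of 28% with 3%, which is natural for T2. It would fall to between 7% and 53% for a separate T3 proportion at 26 per arm, if new discussions after T2 run at 8% to 20% against 3%. Those rates are illustrative, as is the choice of the uncorrected chi-square test. What does not rest on them is the undefined primary comparison and the index visit's absence from the T3 answer; both follow from sections 5.1, 5.5 and 5.6 as written.

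**What to change.** In section 5.6, name patient-reported CKM discussion at T2 as the single primary comparison, and tie the 3% rate, the alpha and the power to it. Report T3 as secondary, defined cumulatively as a yes at T2 or at T3.

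A single cumulative outcome by T3 is an acceptable primary instead. The period to which the 3% refers, and the power, would then have to be restated (step 5).

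The cost is protocol wording: no new visit, no new item and no change to the 76 patients. The downside is that the separate T3 comparison is no longer primary.

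Handling of a missed report can be left to the analysis plan, with one caution. A rule that keeps a T2 yes when T3 is missing but sets a T2 no to missing removes only non-events. For illustration, assume a true cumulative 28% against 3%, every T3 yes repeating a T2 yes, and 30% missing T3. The estimates become 28/(28 + 72 × 0.7) = 35.7% and 3/(3 + 97 × 0.7) = 4.2%, a difference of 31.5 points instead of 25.
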